5.6. Intervention After the End of the Study

Any SAE occurring after a participant's scheduled EOS and considered to be caused by the vaccine must be reported to the Sponsor.

6. DELAYING OR DISCONTINUING STUDY TREATMENT AND PARTICIPANT WITHDRAWAL FROM THE STUDY

6.1. Criteria for Delay of Vaccine Administration

6.1.1. Individual Participant Criteria for Delay of Study Vaccination

Body temperature (oral) must be measured on dosing visits before vaccine administration. The following events constitute criteria for delay of injection, and if either of these events occur at the time scheduled for dosing, the participant may receive the study injection at a later date within the time window specified in the applicable SoE ([Section 10.1](#)), or the participant may be discontinued from dosing at the discretion of the investigator ([Section 6.2](#)):

- Acute moderate or severe infection with or without fever at the time of dosing
- Fever, defined as body temperature $\geq 38.0^{\circ}\text{C}/\geq 100.4^{\circ}\text{F}$ at the time of dosing (oral temperature preferred)

Participants with a minor illness without fever, as assessed by the investigator, can be vaccinated. Participants with a fever of $\geq 38.0^{\circ}\text{C}/\geq 100.4^{\circ}\text{F}$ will be contacted within the time window acceptable for participation and re-evaluated for eligibility. If the investigator determines that the participant's health on the day of dosing temporarily precludes injection, the visit should be rescheduled within the allowed interval for that visit if possible or at a time the participant is clinically stable according to the judgement of the investigator.

If a participant takes a prohibited drug therapy, an injection could be delayed within the visit window based on the joint decision of the investigator and the CRO's medical monitor ([Section 5.5.3](#)).

6.2. Discontinuing Study Vaccination

Participants can discontinue study injection (ie, refuse the second or third dose) for any reason, without prejudice to further treatment the participant may need to receive.

The investigator, in consultation with the Sponsor's medical monitor, may withhold a participant from further injection if the participant does any of the following:

- Withdraws consent to participate in the study ([Section 6.3](#))
- Becomes pregnant ([Section 7.5.5](#))
- Develops, during the course of the study, symptoms or conditions listed in the exclusion criteria ([Section 4.1.1.2](#) or [Section 4.1.2.2](#))

- Experiences an unsolicited AE (other than reactogenicity) after injection that is considered by the investigator to be related to vaccine ([Section 7.5.10](#)) and is assessed as severe ([Section 7.5.9](#))
- Experiences an AE or SAE that, in the judgment of the investigator, requires vaccine withdrawal due to its nature, severity, or required treatment, regardless of the causal relationship to vaccine
- Experiences a clinically significant change in vital sign measurements or general condition that, in the judgment of the investigator, requires vaccine withdrawal
- Experiences anaphylaxis ([Section 7.5.5](#)) clearly related to vaccine
- Experiences an event that meets the criteria for study pause rules ([Section 7.6.2](#))

The reason(s) for withdrawal from further injection will be recorded in the eCRF.

If a participant takes a prohibited drug therapy, the investigator could withhold the second or third dose based on a joint decision of the investigator and the CRO's medical monitor ([Section 5.5.2](#)).

Every reasonable attempt will be made to follow-up with participants for safety throughout the entire scheduled study period according to their regimen, even if the participant does not receive the second or third dose or misses 1 or more visits. Unless participants withdraw consent, they are expected to remain in the study and complete all scheduled visits and assessments.

6.3. Participant Discontinuation/Withdrawal from the Study

Participants who withdraw or are withdrawn from the study will not be replaced. A “withdrawal” from the study refers to a situation wherein a participant does not return for the final visit planned in the protocol. The statistical management of participant withdrawals is discussed in [Section 8](#).

Participants can withdraw consent and withdraw from the study at any time, for any reason, without prejudice to further treatment the participant may need to receive. The investigator will request that the participant complete all study procedures pending at the time of withdrawal.

If the participant desires to withdraw from the study because of an AE, the investigator will try to obtain agreement to follow-up with the participant until the event is considered resolved or stable and will then complete the EOS eCRF.

Information related to the withdrawal will be documented in the eCRF. The investigator will document whether the decision to withdraw a participant from the study was made by the participant or by the investigator, as well as which of the following possible reasons was responsible for withdrawal:

- AE (specify)
- SAE (specify)
- Death
- Lost to follow-up (LTFU)
- Physician decision (specify)
- Pregnancy
- Protocol deviation
- Study terminated by Sponsor
- Withdrawal of consent by participant (specify)
- Other (specify)

Participants who are withdrawn from the study because of AEs (including SAEs) must be clearly distinguished from participants who are withdrawn for other reasons. Investigators will follow-up with participants who are withdrawn from the study as result of an SAE or AE until resolution of the event.

A participant who withdraws from the study may request destruction of any samples taken and not tested, and the investigator must document this in the study site study records.

If the participant withdraws consent for disclosure of future information, the Sponsor may retain and continue to use any data collected before such a withdrawal of consent ([Section 10.2.10](#)).

The Sponsor will continue to retain and use all research data that have already been collected for the study evaluation, unless the participant has requested destruction of these samples. All biological samples that have already been collected may be retained and analyzed at a later date (or as permitted by local regulations)

6.4. Lost to Follow-up

A participant will be considered LTFU if he or she repeatedly fails to return for scheduled visits without stating an intention to withdraw consent and is unable to be contacted by the study site. The following actions must be taken if a participant fails to return to the clinic for a required study visit:

- The study site staff must attempt to contact the participant and reschedule the missed visit as soon as possible, counsel the participant on the importance of maintaining the assigned visit schedule and ascertain whether the participant wishes to and/or should continue in the study.

- Before a participant is deemed LTFU, the investigator or designee must make every effort to regain contact with the participant (where possible, 3 telephone calls, emails, and, if necessary, a certified letter to the participant's last known mailing address or local equivalent methods). These contact attempts (eg, dates of telephone calls, emails, and certified letters) should be documented in the participant's medical record.
- A participant who continues to be unreachable or continues to be noncompliant with study visits or procedures will be considered to have withdrawn from the study.
- A participant should not be considered LTFU until due diligence has been completed.

7. STUDY ASSESSMENTS AND PROCEDURES

Before performing any study procedures, all potential participants will sign an ICF (as detailed in [Section 10.2.6](#)). Participants will undergo study procedures at the time points specified in the applicable SoE ([Section 10.1](#)). A participant can also be seen for an unscheduled visit at any time during the study. An unscheduled visit may be prompted by reactogenicity issues, illness visit criteria for COVID-19, or new or ongoing AEs. The study site also has the discretion to make reminder telephone calls or send text messages to inform the participant about visits, review eDiary requirements, or follow-up on ongoing or outstanding issues.

In accordance with “FDA Guidance on Conduct of Clinical Trials of Medical Products during COVID-19 Public Health Emergency” ([DHHS 2020](#)), investigators may convert study site visits to telemedicine visits with the approval of the Sponsor. Such action should be taken to protect the safety and well-being of study participants and study site staff or to comply with state or municipal mandates.

General considerations for study assessments and procedures include the following:

- Protocol waivers or exemptions are not allowed. The study procedures and their timing must be followed as presented in [Section 10.1](#). Adherence to the study design requirements is essential and required for study conduct.
- Immediate safety concerns should be discussed with the Sponsor immediately upon occurrence or awareness to determine if the participant should continue study treatment or participation in the study.
- All screening evaluations must be completed and reviewed to confirm that potential participants meet all eligibility criteria. The investigator will maintain a screening log to record details of all participants screened and to confirm eligibility or record reasons for screening failure, as applicable.
- Procedures conducted as part of the participant’s routine clinical management (eg, blood count) and obtained before signing of the ICF may be utilized for screening or baseline assessments provided the procedures met the protocol-specified criteria and were performed within the time frame defined in the applicable SoE.

7.1. Safety Assessments and Procedures

Safety assessments will include monitoring and recording of the following for each participant, according to the applicable SoE:

- Solicited local and systemic ARs ([Section 7.5.3](#)) that occur during the 7 days following each injection (ie, the day of injection and 6 subsequent days). Solicited

ARs will be recorded daily using the eDiary ([Section 7.1.1](#)). The definition of AR is presented in [Section 7.5.1](#).

- Unsolicited AEs observed or reported during the 28 days following each injection (ie, the day of injection and 27 subsequent days). Unsolicited AEs are defined in [Section 7.5.1](#).
- MAAEs throughout the study period.
- SAEs throughout the study period.
- AESIs throughout the study period.
- AEs leading to discontinuation from dosing and/or study participation (withdrawal) throughout the study period.
- Biopsy-proven organ rejection throughout the study period. A biopsy report will be needed for documentation.
- Safety laboratory assessments:

Part A

- For unvaccinated SOT recipients who receive the 2-dose regimen (Group A1), safety laboratory assessments related to kidney (for kidney transplant recipients) and liver function (for liver transplant recipients) will be monitored on Day 1, Day 8, Day 29, Day 36, and Day 57. After Day 57, the investigator will review standard-of-care laboratory assessments related to kidney and liver function (as related to the SOT) and report any laboratory-related AEs and suspected or confirmed events of organ transplant rejection until the EOS.
- For unvaccinated SOT recipients who receive the 3-dose regimen (Group A2), safety laboratory assessments related to kidney (for kidney transplant recipients) and liver function (for liver transplant recipients) will be monitored on Day 1, Day 8, Day 29, Day 36, Day 57, Day 85, Day 92, and Day 113. After Day 113, the investigator will review standard-of-care laboratory assessments related to kidney and liver function (as related to the SOT) and report any laboratory-related AEs and suspected or confirmed events of organ transplant rejection until the EOS.
- For previously vaccinated SOT recipients who receive dose 3 (Group A3), safety laboratory assessments related to kidney (for kidney transplant recipients) and liver function (for liver transplant recipients) will be monitored on Day 1, Day 8, and Day 29. After Day 29, the investigator will review standard-of-care

laboratory assessments related to kidney and liver function (as related to the SOT) and report any laboratory-related AEs and suspected or confirmed events of organ transplant rejection until the EOS.

Part B

- For SOT participants who completed primary vaccination series (Group B2, Group B3, and Group B4), safety laboratory assessments related to kidney (for kidney transplant recipients) and liver function (for liver transplant recipients) will be monitored on BD-D1, BD-D8, and BD-D29. After BD-D29, the investigator will review standard-of-care laboratory assessments related to kidney and liver function, and report any laboratory-related AEs and suspected or confirmed events of organ transplant rejection until the EOS.
- Vital sign measurements ([Section 7.1.4](#)).
- Physical examination findings ([Section 7.1.5](#)).
- Assessments for SARS-CoV-2 infection from Day 1 through study completion ([Section 7.1.6](#)).
- Details of all pregnancies in female participants will be collected after the start of study treatment and until the end of their participation in the study ([Section 7.5.5](#)).
- Changes in immunosuppressant medications in SOT recipients

7.1.1. Use of Electronic Diaries

At the time of consent, participants must confirm that they will be willing to complete an eDiary using either an application downloaded to their smartphone or using a device that is provided at the time of enrollment. Before enrollment on Day 1, participants will be instructed to download the eDiary application or will be provided an eDiary device to record solicited ARs ([Section 7.5.3](#)) on Day 1.

At each injection visit, participants will be instructed on thermometer usage to measure body temperature, ruler usage to measure injection site erythema and swelling/induration (hardness), and self-assessment for localized axillary swelling or tenderness on the same side as the injection arm.

At each injection visit, participants will record data into the eDiary starting approximately 30 minutes after injection under supervision of the study site staff to ensure successful entry of assessments. The study site staff will perform any retraining as necessary. Participants will continue to record data in the eDiary after they leave the study site, preferably in the evening and at the same time each day, on the day of injection and for 6 days following injection.

Participants will record the following data in the eDiary:

- Solicited local and systemic reactogenicity ARs, as defined in [Section 7.5.3](#), that occur on the day of each vaccine administration and during the 7 days after vaccine administration (ie, the day of injection and 6 subsequent days). If a solicited local or systemic AR continues beyond Day 7 after vaccination, the participant will be prompted to capture details of the solicited local or systemic AR in the eDiary until it is resolved or the next vaccine injection occurs, whichever occurs first; capture of details of ARs in the eDiary should not exceed 28 days after each vaccination. Adverse reactions recorded in the eDiary beyond Day 7 should be reviewed by the study site staff either during the next scheduled telephone call or at the next study site visit.
- Daily oral body temperature measurement should be performed at approximately the same time each day using the thermometer provided by the study site. If body temperature is taken more than once in a given day, only the highest temperature reading should be recorded.
- Measurement, as applicable, for solicited local ARs (injection site erythema and swelling/induration); the size measurements will be performed using the ruler provided by the study site.
- Any medications taken to treat or prevent pain or fever on the day of injection or for the next 6 days.

The eDiary will be the only source documents allowed for solicited local or systemic ARs (including body temperature measurements). Participants will be instructed to complete eDiary entries daily. The participant will have a limited window on the following day to complete assessments for the previous day; quantitative temperature recordings and measurement of any injection site erythema or swelling/induration reported on the following day may be excluded from the analyses of solicited ARs.

Any new safety information reported during safety telephone calls or at study site visits (including a solicited reaction) that is not already captured in the eDiary will be described in the source documents as a verbally reported event. An event reported in this manner must be described as a solicited event and entered on the solicited AR eCRF.

Study site staff will review eDiary data with participants at visits 7 days after each injection.

In Part A, the eDiary will also be used every 4 weeks to capture the occurrence of AEs, MAAEs, SAEs, AESIs, or AEs leading to discontinuation from dosing and/or study participation (withdrawal) as follows:

- Starting at Day 71 through Day 183 and again starting at Day 223 through Day 363 for unvaccinated SOT and healthy recipients of 2 vaccine doses (Group A1 and Group A5),
- Starting at Day 127 through Day 239 and again Day 279 through Day 419 for unvaccinated SOT recipients of 3 vaccine doses (Group A2), and
- Starting at Day 43 through Day 155 and again starting at Day 194 through Day 306 (previously vaccinated SOT recipients who receive dose 3) (Group A3).

The timing of eDiary prompts and safety calls will not be adjusted when the last dose is delayed. If the last dose is delayed beyond the standard window, the following clinic visits should be adjusted:

For the 2-dose regimen (Group A1 and Group A5), the actual date of the last delayed dose should be used to adjust D36 (7 days after last dose), D57 (28 days after last dose), 6 months visit (180 days after last dose) and 12 months visit (365 days after last dose).

For the 3-dose regimen (Group A2), the actual date of the last delayed dose should be used to adjust dates for D97 (7 days after last dose), D113 (28 days after last dose), 6 months visit (180 days after last dose) and 12 months visit (365 days after last dose).

Additional safety calls every 4 weeks should be scheduled when there is a gap beyond 28 days between the safety call scheduled on D377 (for 2 doses [Group A1 and Group A5]) or D433 (for 3 doses [Group A2]) and the last study visit.

As specified in the applicable SoE, the eDiary will prompt the participant to complete an eDiary questionnaire that collects the following data:

- Changes in health since last completing the questionnaire or since in contact with the study site
- Known close contact exposure to someone with known COVID-19 or SARS-CoV-2 infection
- Any experience of symptoms of COVID-19
- Any MAAEs or SAEs

If an eDiary record results in identification of relevant safety events according to the study period, or of symptoms of COVID-19, a follow-up safety telephone call will be triggered.

Completion of eDiary questionnaires will alternate with safety telephone calls ([Section 7.1.2](#)) as the procedure for safety follow-up approximately every 4 weeks:

- Starting at Day 85 through Day 197 and again starting at Day 237 through Day 377 for unvaccinated SOT and healthy recipients of 2 vaccine doses (Group A1 and Group A5),

- Starting every 4 weeks from Day 141 through Day 253 and again from Day 293 through Day 433 for unvaccinated SOT recipients of 3 vaccine doses (Group A2), and
- Starting at Day 57 through Day 169 and again starting at Day 208 through Day 320 (previously vaccinated SOT recipients who receive dose 3) (Group A3).

The follow-up eDiary questionnaires and the safety calls conducted by the study staff will occur ~2 weeks apart on a 4 week cycle.

7.1.1.1. Ancillary Supplies for Participant Use

Study sites will distribute Sponsor-provided oral thermometers and rulers for use by participants in assessing body temperature and injection site reactions, respectively, for recording solicited ARs in the eDiary. Based on availability, smartphone devices may be provided to those participants who do not have their own device to use for eDiary activities.

7.1.2. Safety Telephone Calls

A safety telephone call is a telephone call made to the participant by trained study site personnel. This call will follow a script, which will facilitate the collection of relevant safety information. In Part A, safety telephone calls follow a schedule for each participant as indicated in the applicable SoE:

- Every 4 weeks from Day 85 to Day 197 and again from Day 237 to Day 377 for unvaccinated SOT and Healthy recipients of 2 vaccine doses (Group A1 and Group A5),
- Every 4 weeks from Day 141 to Day 253 and again from Day 293 to Day 433 for unvaccinated SOT recipients of 3 vaccine doses (Group A2), and
- Every 4 weeks from Day 57 through Day 169 and again starting at Day 208 through Day 320 for previously vaccinated SOT recipients who receive dose 3 (Group A3).

The schedule of safety telephone calls will not be adjusted for each participant based on the actual day of the last dose, if delayed. Additional safety calls every 4 weeks should be scheduled when there is a gap beyond 28 days between the safety call scheduled on D377 (for 2 doses [Group A1 and Group A5]) or D433 (for 3 doses [Group A2]) and the last study visit.

In Part B, safety telephone calls will be performed on BD-D15, BD-D22, BD-D59, BD-D89, BD-119, and BD-D149 to collect information about occurrence of AEs, MAAEs (including biopsy-proven organ rejection), SAEs, AESIs, AEs leading to discontinuation from dosing and/or study participation (withdrawal), concomitant medications associated with those events, and any nonstudy vaccinations ([Section 7.5.8](#)).

The participant will be interviewed according to the script about occurrence of AEs, MAAEs (including biopsy-proven organ rejection), SAEs, AESIs, AEs leading to discontinuation from dosing and/or study participation (withdrawal), concomitant medications associated with those events, and any nonstudy vaccinations ([Section 7.5.8](#)). In addition, study personnel will collect information on known participant close contact exposure to someone with known COVID-19 or SARS-CoV-2 infection and on participant experience of COVID-19 symptoms. All safety information collected from the telephone contact must be documented in source documents as described by the participant and not documented on the script used for the safety telephone contact. As noted in [Section 7.1.1](#), an unscheduled follow-up safety telephone call may be triggered if an eDiary record results in identification of a relevant safety event.

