3.1.1.2. Treatment Period and Follow-up Period

The Treatment Period for each participant starts with Day 1 and is scheduled to end 28 days after each dose of vaccine. In Part A, for unvaccinated SOT and healthy participants who receive the 2-dose regimen (Group A1 and Group A5), the Follow-up Period starts with Day 58 and is scheduled to end on Day 394 (12 months after the second dose). The Follow-up Period for unvaccinated SOT participants who receive the 3-dose regimen (Group A2) starts with Day 114 and is scheduled to end on Day 450 (12 months after the third dose). The Follow-up Period for previously vaccinated participants (Group A3) starts with Day 29 and is scheduled to end on Day 365 (12 months after dose 3). In Part B (Group B2, Group B3, Group B4, and Group B5), Follow-up Period starts with Day 29 and is scheduled to end on BD-D181 (6 months after BD).

For Part A (Group A1, Group A2, Group A3, and Group A5): On Day 1, after the completion of the scheduled assessments ([Section 10.1](#)), all participants will be administered a single IM dose of 100 μ g of mRNA-1273 ([Section 5.3.2](#)). Participants will be closely monitored for safety and will remain at the study site for observation for at least 30 minutes after dosing. For unvaccinated SOT and healthy participants (Group A1, Group A2, and Group A5), the second dose of vaccine will be administered on Day 29. Unvaccinated SOT recipients who consent to receive a third dose of

vaccine (Group A2) will receive it on Day 85. Previously vaccinated SOT recipients (Group A3) will receive dose 3 on Day 1. Participants will be monitored for 12 months after the second and third dose (as applicable) of vaccine for safety, immunogenicity, and breakthrough SARS-CoV-2 infection or COVID-19.

For Part B (Group B2, Group B3, Group B4, and Group B5): On BD-D1, after the completion of the scheduled assessments, at least 4 months after the last dose, all participants will be administered a single intramuscular (IM) dose of 100 µg BD of mRNA-1273. Participants will be closely monitored for safety and will remain at the study site for observation for at least 30 minutes after dosing. Participants will be monitored for 6 months after the BD for safety, immunogenicity, and breakthrough SARS-CoV-2 infection or COVID-19.

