2. All scheduled study visits should be completed within the respective visit windows. If the participant is not able to attend a study site visit as a result of the COVID-19 pandemic (self-quarantine or disruption of study site activities following business continuity plans and/or local government mandates for “stay at home” or “shelter in place”), a safety telephone call to the participant should be made in place of the study site visit. The safety telephone call should encompass all scheduled visit assessments that can be completed remotely, such as assessment for AEs and concomitant medications (eg, as defined in scheduled safety telephone calls). Telemedicine will be permitted for all nondosing visits, with the exception of Screening, if a participant cannot visit the study site as a result of the COVID-19 pandemic. Telemedicine visits must be permitted by the study site IRB and the participant via informed consent and have prior approval from the Sponsor (or its designee). Participants who agree to receive a booster dose in Part B will follow the schedule of events for Part B (see [Table 10](#)).
3. Safety follow-up via an eDiary questionnaire will be performed every 4 weeks from Day 43 to Day 155 and again from Day 194 to Day 306.
4. Safety follow-up via a safety telephone call will be performed every 4 weeks from Day 57 to Day 169 and again from Day 208 to Day 320.

5. Physical examination: A full physical examination, including height and weight, will be performed to determine eligibility prior to administration of vaccine dose on Day 1. Body mass index will be calculated only at the screening visit (Day 0). Symptom-directed physical examinations will be performed at Day 29, Day 180, and Day 365. Any clinically significant finding identified during a study visit should be reported as an MAAE.
6. On the injection day before injection and again 7 days after injection, the arm that received the injection should be examined and the associated lymph nodes must be evaluated. Any clinically significant finding identified during a study visit should be reported as an MAAE.

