### 6.5.1.3.COVID-19

The incidence of the first occurrence of COVID-19 starting 14 days after the second, third dose, and BD of IP will be presented. COVID-19 is defined as symptomatic disease based on the criteria specified in [Section 3.2.2](#). Cases are defined as participants meeting clinical criteria based on both symptoms for COVID-19 and positive RT-PCR test results.

Surveillance for COVID-19 symptoms will be conducted every two weeks by either telephone calls or eDiary prompts (alternating). Subjects reporting COVID-19 symptoms, as defined in Section 7.3.2 of Protocol Amendment 4, will be arranged an illness visit to collect an NP swab.

For this endpoint, a COVID-19 case will be identified as a positive post-baseline RT-PCR test result, together with eligible symptoms as described below in [Table 2](#).

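### Unboosted Group A3 participants have a nominal 45 days without scheduled contact before the Day 365 visit, because their second follow-up series is one 4-week cycle shorter than in the other Part A groups

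*Protocol*

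**What the plan says.** Part A follow-up uses two alternating contact types, each on a 4-week cycle: an eDiary questionnaire and a scripted safety call. Protocol 7.1.1 says that these "will occur ~2 weeks apart on a 4 week cycle". SAP 6.5.1.3 relies on the same spacing for case finding: "Surveillance for COVID-19 symptoms will be conducted every two weeks by either telephone calls or eDiary prompts (alternating".

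For Group A3, protocol 7.1.2 gives the calls: "Every 4 weeks from Day 57 through Day 169 and again starting at Day 208 through Day 320 for previously vaccinated SOT recipients". Table 9, footnote 3, gives the eDiary prompts: "every 4 weeks from Day 43 to Day 155 and again from Day 194 to Day 306". Protocol 3.1.1.2 fixes the end: "The Follow-up Period for previously vaccinated participants (Group A3) starts with Day 29 and is scheduled to end on Day 365".

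For Groups A1 and A5, protocol 7.1.2 sets calls "Every 4 weeks from Day 85 to Day 197 and again from Day 237 to Day 377", with the last visit on Day 394. Group A2 has calls on Days 141 to 253 and 293 to 433, with the last visit on Day 450.

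The A3 days are the same in the synopsis, 3.1.1, 7.1.1, 7.1.2, 7.3.1 and Table 9. Section 7.1.2 also asks for extra calls "when there is a gap beyond 28 days between the safety call scheduled on D377" (Groups A1 and A5) or Day 433 (Group A2) and the last visit. It names no day for A3, and Table 9 carries no such footnote.

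**The concern.** The other Part A groups have a contact about every two weeks up to 17 days before the final visit. Group A3 has the same spacing until Day 320 and then nothing scheduled until Day 365. No reason is given, and since the same days recur in every section, sites will follow them.

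The calls and prompts collect medically attended, serious and special-interest events and ask about COVID-19 symptoms and exposure. SAP 6.5.1.3 needs a positive PCR within 14 days of eligible symptoms for a COVID-19 case, and SAP 6.5.2 counts cases in A3 without booster through Day 365. An illness that the participant does not report when it happens, and first recalls at Day 365, may have no PCR. COVID-19 and non-serious medically attended events may therefore be under-ascertained in these participants relative to A1, A2 and A5. A3 is summarised beside those groups and is combined with A2 in the SAP's total for transplant recipients given three doses.

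**Working it through.** Inputs: series start and end days from protocol 7.1.1, 7.1.2 and Tables 7 to 9; call window ±3 days and final-visit window ±14 days from the same tables; the counting window from SAP 6.5.2.

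**1. Reproduce the plan's end days** (start + 28 × number of further cycles).
- A3 eDiary: 194 + 4 × 28 = 306, five prompts. A3 calls: 208 + 4 × 28 = 320, five calls.
- A1/A5 eDiary: 223 + 5 × 28 = 363. Calls: 237 + 5 × 28 = 377. Six of each.
- A2 eDiary: 279 + 5 × 28 = 419. Calls: 293 + 5 × 28 = 433. Six of each.

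All match the protocol. The first series has five prompts and five calls in every group, so only the second A3 series is short.

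**2. Compare the interval to be covered.**

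| Group | 6-month visit | 12-month visit | Interval | First prompt after 6-month visit | Last call | Final gap |
|---|---|---|---|---|---|---|
| A1/A5 | 209 | 394 | 185 | 223 − 209 = 14 | 377 | 17 |
| A2 | 265 | 450 | 185 | 279 − 265 = 14 | 433 | 17 |
| A3 | 180 | 365 | 185 | 194 − 180 = 14 | 320 | 45 |

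Interval and starting offset are identical; only the number of cycles differs. Every other gap between A3 contacts from the Day 43 prompt onward is 14 days, or 11 days from the Day 169 call to the Day 180 visit.

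**3. Apply the windows to all groups.**
- A3: shortest (365 − 14) − (320 + 3) = 28; longest (365 + 14) − (320 − 3) = 62.
- A1/A5: shortest (394 − 14) − (377 + 3) = 0; longest (394 + 14) − (377 − 3) = 34. A2 gives the same 0 to 34.

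**4. Share of the case-counting window.** For A3 without booster the SAP counts Day 15 to Day 365, which is 365 − 15 + 1 = 351 days. 45 / 351 = 12.8%.

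**5. Effect of one more cycle.** eDiary 306 + 28 = 334; call 320 + 28 = 348; final gap 365 − 348 = 17 days, or 0 to 34 with windows, as in the other groups.

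**The case against.** The case against giving this weight is substantial, and most of it stands.

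- **Not all of A3 is affected.** A reader might infer that the whole group has the gap. Table 2 routes A3 to Group B3, with the booster planned around Day 120, and boosted participants follow Table 10 and are counted to BD-Day 181. Only those who stay on Table 9 reach the gap. The documents do not say how many that will be.
- **Surveillance does not stop.** A reader might infer that late illnesses cannot be confirmed. Section 7.3.1 tells participants to report symptoms throughout the study and provides for a swab within 72 hours. Illness visits stay active in Table 9, and standard-of-care kidney and liver results are reviewed to the end of study. An illness reported when it occurs can still be confirmed.
- **Blood is still drawn.** Protocol safety laboratory tests end at Day 29 in A3, but they also end at Day 57 in A1 and Day 113 in A2. Anti-nucleocapsid serology is drawn at Days 180 and 365 and can pick up infection in the gap for the SARS-CoV-2 infection endpoint. It cannot supply the PCR that the COVID-19 endpoint needs.
- **The 28-day rule is not breached.** A reader might infer that A3 violates it or was wrongly left out. The rule is tied to a delayed last dose, and A3's only Part A dose defines Day 1, so that case cannot arise. The rule is context, not a contact standard for A3.
- **Longer intervals are accepted elsewhere.** In Part B the later calls are 30 days apart, and BD-D149 to BD-D181 is 32 days. That is still shorter than 45, and Part B has no follow-up eDiary series from which to fall short.
- **Nothing is tested.** Both documents say that no between-group comparisons are planned, so a biased comparison is not a supported conclusion. What remains is uneven ascertainment in descriptive rates.

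**Conclusion.** The schedule point holds; its consequence is minor. For A3 participants who do not move to Part B, the second series is one prompt and one call short, and the last scheduled contact is nominally 45 days before the final visit, against 17 in A1/A5 and A2. This does not fit the contact spacing stated in protocol 7.1.1 or the surveillance interval in SAP 6.5.1.3. It covers 13% of the counting window for A3 without booster.

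The likely effect is some under-ascertainment of COVID-19 and of non-serious medically attended events first recalled at Day 365. Serious events and biopsy-proven rejection involve healthcare encounters and can still be recorded at that visit. How many events might be missed cannot be estimated, because the documents give neither the number of unboosted A3 participants nor a rate of unprompted reporting. The day counts assume nominal visit days unless a windowed range is given.

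**What to change.** In the synopsis, 3.1.1, 7.1.1, 7.1.2, 7.3.1 and Table 9 (including footnotes 3 and 4), extend the second A3 series by one 4-week cycle: eDiary Day 194 through Day 334 and safety calls Day 208 through Day 348. Adding A3 to the 28-day gap sentence is optional, since the nominal final gap would then be 17 days.

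The cost is schedule wording, one eDiary prompt and one scripted call per unboosted A3 participant, using existing staff. No dose, clinic visit or analysis method changes.
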